COMPARISON OF BENZALKONIUM CHLORIDE CONTAINING ALBUTEROL VERSUS PRESERVATIVE FREE ALBUTEROL FOR THE TREATMENT OF STATUS ASTHMATICUS

BACKGROUND

In 2014, the Centers for Disease Control and Prevention reported approximately 6.3 million children in the United States with a diagnosis of asthma.¹ According to the National Heart, Lung, and Blood Institute, inpatient management of an acute asthma exacerbation may include continuous albuterol administration.² Due to higher dosing requirements over an extended duration of time, continuous albuterol administration requires a larger volume of albuterol solution, which is often obtained from a multi-dose vial containing benzalkonium chloride (BAC). BAC is a common preservative used in pharmaceuticals, but also considered to be a potent bronchoconstrictor. BAC doses as low as 124 micrograms have been shown to cause bronchoconstriction. This effect is cumulative, prolonged, and correlates directly with basal airway responsiveness.³ The multi-dose albuterol vials currently used for continuous albuterol administration contain 50 micrograms of BAC per 2.5 milligrams of albuterol. A patient receiving continuous albuterol inhalation at 20 milligrams per hour will receive 400 micrograms of BAC per hour. In the 1999 study conducted by Asmus et al., the mean concentration of BAC required to provoke a 20% drop in FEV₁ was 300 micrograms (range 124 to 1947 micrograms).⁴ This raises concern that the bronchoconstricting effects of BAC may antagonize the therapeutic goals of albuterol therapy among patients receiving continuous albuterol inhalation for extended periods of time.

OBJECTIVE

The primary objective of this study is to compare the length of continuous albuterol administration between patients receiving BAC-containing albuterol (BAC-albuterol) versus preservative free albuterol (PF-albuterol). Secondary objectives include comparison of therapy escalation, asthma scores, forced expiratory volume in one second (FEV₁) at discharge, length of hospital stay, and cost.

METHODS

A prospective, patient-blinded, randomized study will be conducted comparing patients admitted to Norton Children's Hospital for an asthma exacerbation. There will be no active recruitment of patients; however, eligible patients will be those who present to our emergency department in status asthmaticus. Patients will be randomly assigned to a patient room on 5 West versus 5 East upon admission based on bed availability. The Pyxis on 5 West will contain the standard multi-dose albuterol vial which contains BAC (current standard of care), while pharmacy will be preparing and dispensing PF-albuterol to patients on 5 East who are enrolled in the study. The treatment of patients will not vary between groups, nor deviate from the standard of care currently implemented at the institution. If a patient consents to study enrollment, he/she will receive PF-albuterol while awaiting bed assignment in the emergency department. This is essential to avoid confounding the results of the study, as BAC has a

prolonged half-life and may have clinical consequences even after a patient is randomized to receive PF-albuterol.

Informed consent will be required for all patients, and assent will additionally be required for patients between 7 and 17 years of age. The study will be explained by a study investigator or respiratory therapist (under the supervision of the respiratory therapy director) and informed consent/assent paperwork will be provided to the patient/caregiver while in the emergency department. Approximately 10-20 minutes will be allotted for the consent/assent process. The difference between groups is the formulation of albuterol being used, and both formulations have FDA approval for use in status asthmaticus.

INCLUSION AND EXCLUSION CRITERIA

Patients will be included in the study if they are admitted to the 5th floor at Norton Children's Hospital for the treatment of an acute asthma exacerbation, initiated on continuous albuterol inhalation therapy, and are between 3 and 17 years of age.

Patients will be excluded from the study if they are transferred to the 5th floor from any other unit except the emergency department, admitted for any indication other than acute asthma exacerbation, or exposed to BAC prior to admission.

DATA COLLECTION

Demographic information collected will include age, gender, weight, and ethnicity.

Data gathered pertaining to continuous albuterol administration will include albuterol formulation, dose, length of therapy, cost of medication administered, and amount of BAC administered.

Additional parameters obtained will include admission asthma score, escalation of therapy related to asthma exacerbation, time on supplemental oxygen, transfer to higher acuity care, total hospital length of stay, and discharge FEV₁.

A data collection document will be used by the respiratory therapist to collect start/stop time of continuous albuterol, evidence of patient non-adherence, and re-initiation of continuous albuterol. After completion, this document will be stored in a binder, in a cabinet, within a locked office. All data (from the data collection form and from the electronic medical record) collected will be stored in an Excel spreadsheet for data analysis. The data collection sheet to be used is attached. Data collected will be stored on a password protected computer, within a locked office, and will be restricted to the primary investigator. All information will be de-identified once entered into the data collection sheet.

STATISICAL ANALYSIS

A power analysis will be conducted in order to determine the sample size needed to detect a statistical difference between groups. Descriptive statistics will be used to evaluate population demographics, while comparison data will be analyzed using a two-tailed student t-test.

CITATIONS

1. National Center for Health Statistics. Asthma, United States, 2014: Morbidity: Children (under age 18 years). Hyattsville, Maryland. 2014
2. Guidelines for the Diagnosis and Management of Asthma (EPR-3). NHLBI, NIH. National Institutes of Health, July 2007

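### The study is called randomized, but the only allocation mechanism given is bed availability, and because formulation follows location the trial data cannot separate the two

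*Combined protocol and SAP*

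**What the plan says.** METHODS opens with the design label: "A prospective, patient-blinded, randomized study will be conducted". It later refers to BAC exposure that "may have clinical consequences even after a patient is randomized to receive PF-albuterol". The only allocation step described is: "Patients will be randomly assigned to a patient room on 5 West versus 5 East upon admission based on bed availability".

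Formulation is then fixed by side. The dispensing cabinet on 5 West holds the BAC-containing multi-dose vial, while "pharmacy will be preparing and dispensing PF-albuterol to patients on 5 East who are enrolled in the study". Before that, a child who has consented is handled alike whichever side is to come: "he/she will receive PF-albuterol while awaiting bed assignment in the emergency department".

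METHODS also asserts that care will be the same in both groups and will follow the institution's existing standard. In the consent paragraph it says: "The difference between groups is the formulation of albuterol being used".

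The primary outcome (OBJECTIVE) is the duration of continuous albuterol. The statistical analysis section plans a two-sided t-test, with no location term and no covariates.

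**The concern.** There are two separate problems.

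**Allocation.** The sentence contradicts itself. It may mean a random choice among open beds, or simply the next free bed. Neither document section gives a sequence, a generator, concealment or an allocation ratio. Bed availability is an operational state that whoever places the patient can see. When only one side has a bed, even the generous reading leaves nothing to randomize.

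**Aliasing.** Among enrolled children, knowing the side tells you the formulation. The groups therefore differ by design in location as well as in formulation, whatever the quality of the allocation.

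What is at stake is the primary comparison. The duration of continuous albuterol depends on when it is stopped. If the two sides differ in stopping practice, or receive different children, the planned t-test would report that difference as an effect of the preservative. More patients would only make the wrong answer look more precise.

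**Working it through.** The plan states no sample size, alpha, SD or expected effect, so there is no figure of its own to reproduce. Step 1 needs only the allocation described in METHODS. Steps 2 and 3 use assumed inputs and show direction only.

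**1. Can formulation be separated from location?**

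Code location (5 West 0, 5 East 1) and formulation (BAC 0, PF 1). Write each patient's design row as (intercept, location, formulation).

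- As written, only two rows occur: (1,0,0) and (1,1,1). The rank is 2 for 3 parameters. The difference in means estimates formulation effect + location effect, and nothing in the trial data splits the sum.
- With a list stratified by location, all four rows occur: (1,0,0), (1,0,1), (1,1,0), (1,1,1). The rank is 3 of 3, so formulation is estimable.
- With a single swap of formulations between sides (intercept, location, period, formulation), the rank is 4 of 4. Adding a location-by-period term gives 4 of 5, so the swap works only if that term is zero.
- With P switching periods there are 2P cell means and P + 2 parameters, leaving 2P − (P + 2) = P − 2 residual degrees of freedom: 0 for a single swap, 2 for four periods, 4 for six and 6 for eight. A single swap cannot check its own assumption.

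**2. What would a location difference do to the planned test?**

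Assume no formulation effect, a two-sided 5% test, n children per location and a location difference of d SD. The t statistic is noncentral with 2n − 2 degrees of freedom and noncentrality d × √(n/2). For n = 50 and d = 0.2 this is 0.2 × √25 = 1.0, which gives 16.8% false positives.

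| n per location | d = 0 | d = 0.1 | d = 0.2 | d = 0.3 |
|---|---|---|---|---|
| 25 | 5.0% | 6.4% | 10.7% | 18.0% |
| 50 | 5.0% | 7.9% | 16.8% | 31.8% |
| 100 | 5.0% | 10.8% | 29.1% | 56.0% |

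Simulation at n = 50 (40,000 runs per cell) agrees: 5.0, 7.7, 16.7 and 31.6%. The mean estimate was 0.00, 0.10, 0.20 and 0.30 SD, so the bias equals the location difference.

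**3. Do the alternatives repair it?**

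- List stratified by location, location in the model, same four location differences: 5.0, 5.1, 5.0 and 5.0% false positives, with a mean estimate of 0.00 each time.
- Switching designs with location and period terms, location difference 0.2 SD, and a location-by-period effect of the ICC shown:

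| Design | ICC 0 | ICC 0.01 | ICC 0.02 | ICC 0.05 |
|---|---|---|---|---|
| 2 periods, 25 per cell (100 children) | 5.0% | 8.1% | 11.2% | 19.5% |
| 4 periods, 12 per cell (96 children) | 5.1% | 6.4% | 7.7% | 12.0% |
| 10 periods, 5 per cell (100 children) | 5.1% | 5.5% | 6.1% | 7.9% |

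**The case against.** The best defence is that METHODS promises the same care in both groups and that the two sides may be one ward in practice. The exclusion criteria treat the floor as a single unit, barring children "transferred to the 5th floor from any other unit except the emergency department", and the documents do not say whether staff are shared. Consent comes before bed assignment, which limits selective enrolment by arm. The admission asthma score is collected, so case mix can be partly examined. If the sentence means a random choice among open beds, chance would balance case mix. Tying formulation to location also guards against mix-ups. And the line that formulation is what differs between groups closes a consent paragraph, so it need not be read as a statistical claim.

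Much of this stands as a limit on size: bias is possible, not shown, and a location effect may be small or zero. It does not answer the point. The promise of equal care is an assertion with no control behind it. The data that could test it (dose, escalation, oxygen time, transfer) arise after assignment, and formulation may affect some of them. Pre-study or non-enrolled records could inform a location difference, but the plan does not use them. Consent order and the admission score bear on case mix, not on a location effect, and no adjustment is planned. Even a true lottery for beds would compare formulation plus location.

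One further limit is fair. Only the patient is described as blinded. A list stratified by location removes location bias, but not any effect of staff knowing the formulation, which is a separate issue.

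**Conclusion.** The concern holds and must be fixed before enrolment. Two findings rest on the text and the rank calculation alone: the plan claims randomization without describing a random mechanism, and formulation is completely aliased with location among enrolled children. No sample size or covariate adjustment can undo the second within the trial data.

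How much this would distort the result is unknown. Any location difference enters the formulation estimate one-for-one. With 50 children per location, differences of 0.1 to 0.3 SD would raise false positives from 5% to between 8% and 32%, but the location difference, alpha and sample size are all assumed. The severity does not depend on those figures.

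**What to change.** Replace the bed-availability sentence in METHODS, and bring the stocking sentence after it into line, with text such as:

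> After consent, confirmed eligibility and bed assignment, pharmacy opens the next assignment on a concealed, computer-generated list stratified by location (5 West, 5 East). The list, not the location, determines the formulation, and both formulations are available on both sides. Location is recorded and included in the primary analysis.

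This fits the present flow, since consented children all receive the same product until a bed is assigned. Adjusting also for the admission asthma score is an optional gain in precision.

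If that is not workable, in order of preference:

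- **Switch formulations between sides over several periods**, and analyse with location and period terms. A single swap is not enough unless a location-by-period effect can be ruled out.
- **Keep formulation tied to location but draw the side by a documented, concealed procedure** when both sides have a bed. Placement in those cases is then random, but the result compares formulation plus location and must be reported so.
- **Keep the present arrangement** and drop the word randomized. Describe a non-randomized comparison of two locations, adjust for admission asthma score and age, and limit the conclusions.

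The main option costs a protocol amendment and a pharmacy-held list; pharmacy already prepares PF-albuterol for enrolled patients. Its real downside is that having both products on both sides creates a mix-up risk that location now limits, so a patient-level label check is needed. The relabelling option costs only wording and an adjusted analysis of data already collected.

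### Does the transfer exclusion drop enrolled children who go to higher-acuity care and come back to the 5th floor?

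*Combined protocol and SAP*

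**What the plan says.** Under Inclusion and Exclusion Criteria the protocol states: "Patients will be excluded from the study if they are transferred to the 5th floor from any other unit except the emergency department". The inclusion sentence just before it is an entry condition: "Patients will be included in the study if they are admitted to the 5th floor at Norton Children's Hospital". The remaining exclusions are admission for another indication and being "exposed to BAC prior to admission".

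Under Methods, "informed consent/assent paperwork will be provided to the patient/caregiver while in the emergency department", and the wing (5 West for BAC-albuterol, 5 East for PF-albuterol) is settled on admission.

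Under Data Collection, the recorded items include "transfer to higher acuity care, total hospital length of stay", and the respiratory therapist's form is used to "collect start/stop time of continuous albuterol, evidence of patient non-adherence, and re-initiation of continuous albuterol". Under Objective, "Secondary objectives include comparison of therapy escalation, asthma scores".

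The text defines no analysis population. It does not say whether an enrolled child who leaves the 5th floor and returns is kept or withdrawn, or how albuterol hours on another unit count. The data collection sheet is described as attached but is not in the supplied text.

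**The concern.** The BAC exclusion has a time limit and the transfer exclusion in the same sentence has none. Consent is sought in the emergency department, so the transfer rule can reach only those consented children who were in some other unit after leaving it. Some were there before first reaching the 5th floor. They have no wing yet, and dropping them does no harm. Others left the 5th floor for higher-acuity care and came back, and they have already been assigned. The wording does not separate the two groups.

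If the second group were dropped, children would be removed after assignment because of something that happened to them on treatment. The Background argues that BAC works against albuterol. If so, more children with long courses might escalate on 5 West and then disappear from the data. The difference in duration would shrink, and some of the transfers that the study records would vanish with the children who had them.

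**Working it through.** **Which reading the text supports**

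1. *Position.* The sentence is under the eligibility heading, next to conditions that are all settled at entry. The exclusion for another indication has no time limit either, and nobody would apply it after assignment.
2. *The contrast with the BAC criterion.* That criterion needs its time limit because children on 5 West receive BAC by design once admitted. The transfer rule has no such need, so its missing limit says little about intent.
3. *Redundancy.* The rule overlaps with consent in the emergency department, but the exclusion for another indication also only restates an inclusion criterion. The transfer rule still has a use before assignment: a child who goes from the emergency department to another unit and only then to the 5th floor.
4. *Data collected.* Transfer to higher-acuity care and re-initiation of continuous albuterol are recorded for study patients. That makes sense if transferred children remain in the data.

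All four points favour route of first arrival.

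**What the literal reading would cost**

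The documents give no sample size, course length, transfer rate or return rate, so there is no figure to reproduce. Every input below is an assumption.

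- PF duration is lognormal, median 14 h, SD of log duration 0.7. Its mean is 14 × exp(0.7²/2) = 14 × exp(0.245) = 17.9 h.
- The BAC median is 1.2 times the PF median, so the mean is 1.2 × 17.9 = 21.5 h. The true difference is 3.6 h.
- The log-odds of transfer rise by b per SD of log duration, on one scale for both arms. The intercept gives 5% transfer in the PF arm.
- A share r of transferred children return and are removed. All others keep their full duration.

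The BAC transfer rate then follows from the longer courses. Numerical integration gives:

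| b | BAC transfer rate | Difference seen, r = 0.5 | Difference seen, r = 1 |
|---|---|---|---|
| 0 | 5.0% | 3.6 h | 3.6 h |
| 0.5 | 5.7% | 3.5 h | 3.5 h |
| 1 | 6.3% | 3.4 h | 3.2 h |
| 1.5 | 6.8% | 3.3 h | 2.9 h |

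With 300 children per arm, which gives about 80% power for 3.6 h with all children kept (two-sided 5% level, assumed), power at b = 1.5 is about 78% (r = 0.5) or 76% (r = 1). With PF transfers at 10%, b = 1.5 and all returning, the difference is 2.6 h and power 71%. With no true effect on duration the transfer rates are equal, and removal creates no difference.

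**Transfer events**

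If a proportion p is transferred, the rate left after removal is (1 − r)p / (1 − rp). For p = 5%:

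- r = 0.5: 0.025 / 0.975 = 2.6%
- r = 0.9: 0.005 / 0.955 = 0.5%
- r = 1: 0

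The share of events lost equals the share who return, which the documents do not give. Children discharged from the other unit, or still there, are not touched even by the literal wording.

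**The case for a change.** The strongest case for a change is that intent is inferred, not written. With no analysis population defined, nothing explicit stops whoever prepares the spreadsheet from dropping returners, perhaps after seeing outcomes, and a clarifying phrase would cost almost nothing. The losses could also be larger than the table shows. If transfers were 5% on PF and 15% on BAC, with b = 1.5, a true 3.6 h would appear as 2.7 h (half return) to 1.5 h (all return), and power at 300 per arm would fall to between 60% and 29%. If all returned, 15 versus 45 expected transfers would become none. With those unequal rates, no effect on duration and all returning, removal would even create a spurious difference of about 1.2 to 1.5 h in favour of BAC (b of 1 to 1.5).

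The missing time limit is real, and so is the direction of the harm if the rule were applied literally. The size does not carry over. A 15% rate on BAC is put in by hand. The stated route, in which BAC lengthens courses and longer courses transfer, gives 5.7% to 6.8%. The severe figures need a further BAC effect on transfer of which the documents give no indication, and they also need the less natural reading of the sentence.

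How off-unit or re-initiated hours count is likewise unstated in the supplied text, but the attached form may settle it. Start and stop times and re-initiation are recorded, and the electronic medical record is a named source, so the hours can be recovered. A common clock start, emergency-department hours by arm and covariate adjustment are separate matters that do not arise from this exclusion.

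**Conclusion.** No change follows. The transfer exclusion has no time limit, but its place among entry conditions and the recording of transfers for study patients make route of first arrival the ordinary reading. A sensible analyst would apply it that way, keep transferred children in the arm assigned, and count their full course. This is a gap in detail, not a demonstrated exclusion after assignment.

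Even under the literal reading, with PF transfers at 5% and longer courses driving transfer, the 3.6 h difference would appear as about 2.9 to 3.5 h. Transfer events would be lost in proportion to the unknown share who return. These figures rest wholly on assumed inputs. The conclusion rests mainly on the reading of the text and would weaken if the attached form, or the study team's practice, showed that returning children are in fact withdrawn.

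### Asthma scores are to be compared between arms, but the only score the text names is the admission score, which is most naturally a baseline

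*Combined protocol and SAP*

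**What the plan says.** The objective section reads "Secondary objectives include comparison of therapy escalation, asthma scores", and goes on to FEV₁ at discharge, length of stay and cost. It gives no scale, time or summary measure for the scores.

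Asthma scores appear only once more, in the data collection section: "Additional parameters obtained will include admission asthma score, escalation of therapy related to asthma exacerbation". The same sentence ends with "total hospital length of stay, and discharge" FEV₁, so the FEV₁ item carries the same time label as its objective. The respiratory therapist's form is described as recording when continuous albuterol starts and stops, non-adherence and restarts; no score is mentioned. The section also says that a data collection sheet is attached and that the electronic medical record is a data source.

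The methods section sets the order of events. Allocation is by ward: "Patients will be randomly assigned to a patient room on 5 West versus 5 East upon admission based on bed availability". Before that, a consenting child is treated alike whichever ward follows: "he/she will receive PF-albuterol while awaiting bed assignment in the emergency department". The exclusion criteria remove children "exposed to BAC prior to admission". Included children "are between 3 and 17 years of age".

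The statistical analysis section gives one method, a two-tailed t-test, for all comparison data, and does not list the variables meant.

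**The concern.** A comparison between formulations needs an outcome measured after the formulations differ. The one score named appears to be measured before they do. If the t-test were applied to it, a null result could be reported as showing that BAC does not affect asthma scores. A difference could be reported as an effect of BAC when it may reflect only which child was given which bed. Neither statement would follow from the data.

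If later scores do exist in the record, a different problem remains. The text does not say which score, on which scale, at what time, answers the objective, so that choice could be made after the data have been seen.

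**Working it through.** The plan states no figure on this point, so there is none to reproduce. The check sets the sections side by side.

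**1. Objectives against data items.**

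| Secondary objective | Item named in data collection | Match |
|---|---|---|
| Therapy escalation | Escalation related to the exacerbation | Yes |
| FEV₁ at discharge | Discharge FEV₁ | Yes |
| Length of hospital stay | Total length of stay | Yes |
| Cost | Cost of the medication given | In part |
| Asthma scores | Admission score | No post-allocation item named |

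Count: 3 matched + 1 matched in part + 1 with an admission item only = 5.

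**2. Order of events.**
- Emergency department: a consenting child receives the preservative-free product, and BAC exposure before admission excludes.
- Admission: the ward is assigned.
- Ward: the formulations differ from here on.

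By the protocol's own design, the arms have no planned difference in BAC exposure up to ward assignment. A score taken at admission therefore most naturally falls before the split. The text does not say whether it is recorded in the emergency department or on the ward. If it were recorded after ward treatment began, some exposure could precede it.

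**3. What a test on the admission score can show.** Let Y₀ be the admission score, Y₁ a later score, and δ the effect of formulation on Y₁. Taking Y₀ as pre-allocation,

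- mean Y₀ on 5 West − mean Y₀ on 5 East = b, the imbalance at allocation;
- δ does not appear in this difference.

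Under valid random allocation b has expectation zero, so the test rejects at about its nominal level whatever δ is. If bed availability produces imbalance, the test picks up b. In neither case does it carry information about δ. A comparison of Y₁ adjusted for Y₀ does target δ: Y₁ = α + δ·(arm) + β·Y₀ + error.

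**4. What is left undefined.** No scale is named, although the ages run from 3 to 17. Admission is a nominal time, but no exact time is given, and no post-allocation time is given for any score.

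The documents give no sample size, significance level, effect size or standard deviation. No error rate or power is attached to this point, and the argument needs none.

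**The case against.** The strongest reply is that the text is not the whole record. The attached sheet was not supplied, and its absence here is not a fault of the plan. The electronic record may hold serial scores. The list of parameters is introduced in a way that need not be exhaustive, and it does not map one-to-one onto the objectives: oxygen duration and transfer to higher acuity care are collected without being named objectives. A reader might infer that no score is taken after allocation. The documents do not support that. They show only that none is named.

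A reader might also infer that the investigators will test the admission score and call the result a treatment effect. The documents do not say so. The statistical section does not assign the admission score to the t-test, and it may be meant purely as a baseline descriptor. If so, however, the objective has no named outcome at all.

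Third, the admission score might be taken after ward treatment has begun. That is possible. The reading as a baseline is an inference from the order of events, and the text does not state it.

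Last, this is one of several secondary outcomes. Escalation, oxygen time, transfer, length of stay and discharge FEV₁ still capture the course after allocation. That limits how much the point matters, but it does not supply the missing definition. The described content of the therapist's form, which includes no score, also gives no positive reason to expect that the sheet fills the gap.

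**Conclusion.** The point holds as a mismatch between one secondary objective and the data named to answer it. As the supplied text stands, one of the five secondary objectives has no named outcome that clearly follows the split in formulation, and its scale and exact scoring time are not given. The one score that is named is most naturally a baseline, so the planned t-test applied to it would check balance only.

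The conclusion assumes that the admission score is recorded before ward treatment starts. It is limited to the supplied text. It does not reach the primary outcome, the length of continuous albuterol, or the other secondary outcomes. It should be corrected before data are analysed, but it does not threaten the trial's main comparison.

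**What to change.** In the data collection and statistical analysis sections:

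1. Name the scoring scale, say when the admission score is recorded relative to the start of ward treatment, and report it as a baseline characteristic.
2. Name one post-allocation score already charted in routine care, within a pre-specified time window after allocation, taken for every child whether or not continuous albuterol is still running. Scores taken only during therapy, or at its stop, should not serve, because their timing depends on the primary outcome.
3. State how children discharged or transferred before that window are handled.
4. Compare this score between arms with adjustment for the admission score, for example by ANCOVA if the scale allows.
5. If the attached sheet already holds such a score, carry its name and time into the text. If none is routinely charted, delete asthma scores from the secondary objectives.

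Where scores are already charted, the cost is some extra data extraction and a few sentences of protocol text. Where they are not, scoring every child at a set time would be a new bedside task, and deletion is cheaper. Two limits remain. Charting times will vary, which is why a window is needed. Scorers may also know the formulation, since the plan says only "A prospective, patient-blinded, randomized study will be conducted" and claims no blinding of staff; that should be stated with the result.
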